## 11.3. Special Instructions for Tests and Assessments

### 11.3.1. Rescreening

Subjects who are not eligible for participation at baseline due to a temporary condition (e.g., acute infection) are allowed to be rescreened once the condition has resolved.

### 11.3.2. Liver Function Test Assessments Prior to Daclizumab Dosing

Before a monthly dose of daclizumab is given, LFT results from prior testing performed within the previous 28 (+3) days must be reviewed by the Study Neurologist or their backup, and must be within protocol-required limits as described in Section 10.5.1.

LFTs can be performed as follows:

- Samples for LFTs must be drawn monthly and will be analyzed centrally for the purposes of this study. This includes any timepoints where there is not a scheduled

CONFIDENTIAL

The information contained herein may not be used, disclosed, or published without the written consent of  
Biogen MA Inc.

study visit and for samples which might be collected outside of the clinic (e.g., by visiting nurses). Accommodations will be made for LFT sampling and central testing for subjects choosing at-home dosing at Month 7, 8, 10 and 11.

- Results from either local or central LFT tests can be used for the medical management of the patient and to determine whether dosing should continue or be suspended at the monthly dosing timepoint (see Section 10).
- In any cases where LFTs are tested locally (e.g., at a local laboratory), samples must also be collected for central analysis for the purposes of this study.
- If the subject is administering daclizumab injections at home, site personnel must contact the subject after review of prior LFT results performed within 28 (+3) days to authorize the monthly injection, or if LFT results warrant, to instruct the subject to withhold their injection.
- LFTs following a treatment suspension must be performed through the central laboratory until the LFT abnormality has resolved. In cases where LFTs cannot be performed via central laboratory, repeat LFT results from local laboratory can be used for confirmation.

#### **11.3.3. MRI Scans**

MRI scan results will be assessed by a central reading center and will **not** be entered into the electronic data capture (EDC) tool. Please refer to the MRI Acquisition and Procedures Manual for a detailed list of results from the central reading center.

#### **11.3.4. Other Assessments**

Vital signs include systolic and diastolic blood pressure, pulse, and body temperature, measured pre-dose. The subject must rest quietly for 5 minutes prior to blood pressure and pulse measurements.

CONFIDENTIAL

The information contained herein may not be used, disclosed, or published without the written consent of Biogen MA Inc.

## **12. SAFETY DEFINITIONS, RECORDING, REPORTING, AND RESPONSIBILITIES**

Throughout the course of the study, every effort must be made to remain alert to possible AEs. If an AE occurs, the first concern should be for the safety of the subject. If necessary, appropriate medical intervention should be provided.

At the signing of the ICF, each subject or his/her legally authorized representative and/or main caregiver must be given the names and telephone numbers of study site staff for reporting AEs and medical emergencies.

### **12.1. Definitions**

#### **12.1.1. Adverse Event**

An AE is any untoward medical occurrence in a subject or clinical investigation subject administered a pharmaceutical product that does not necessarily have a causal relationship with this treatment. An AE can therefore be any unfavorable and unintended sign (including an abnormal laboratory finding), symptom, or disease temporally associated with the use of a medicinal (investigational) product, whether or not related to the medicinal (investigational) product.

Determination of whether an abnormal laboratory value meets the definition of an AE will be made by the Investigator. Although abnormal laboratory values are typically not considered AEs, the following considerations may result in an abnormal laboratory value being considered an AE:

- A laboratory test result that meets the criteria for as SAE.
- A laboratory test result that requires the subject to receive specific corrective therapy.
- A laboratory abnormality that the Investigator considers to be clinically significant.

#### **12.1.2. Serious Adverse Event**

An SAE is any untoward medical occurrence that at any dose:

- results in death,
- in the view of the Investigator, places the subject at immediate risk of death (a life-threatening event); however, this does not include an event that, had it occurred in a more severe form, might have caused death,
- requires inpatient hospitalization or prolongation of existing hospitalization,
- results in persistent or significant disability/incapacity, or
- results in a congenital anomaly/birth defect.

An SAE may also be any other medically important event that, in the opinion of the Investigator, may jeopardize the subject or may require intervention to prevent one of the other outcomes

CONFIDENTIAL

The information contained herein may not be used, disclosed, or published without the written consent of  
Biogen MA Inc.

listed in the definition above. (Examples of such medical events include allergic bronchospasm requiring intensive treatment in an emergency room or convulsions occurring at home that do not require an inpatient hospitalization.)

### **12.1.3. Prescheduled or Elective Procedures or Routinely Scheduled Treatments**

A prescheduled or elective procedure or a routinely scheduled treatment will not be considered an SAE, even if the subject is hospitalized; the study site must document all of the following:

- The prescheduled or elective procedure or routinely scheduled treatment was scheduled (or was on a waiting list to be scheduled) prior to obtaining the subject's consent to participate in the study.
- The condition requiring the prescheduled or elective procedure or routinely scheduled treatment was present before and did not worsen or progress in the opinion of the Investigator between the subject's consent to participate in the study and the time of the procedure or treatment.
- The prescheduled or elective procedure or routinely scheduled treatment is the sole reason for the intervention or hospital admission.
- If a subject is hospitalized due to local requirements for administration of the study treatment, the hospitalization should not be considered an SAE unless 1 of the requirements in Section 12.1.2 is met.

## **12.2. Safety Classifications**

### **12.2.1. Investigator Assessment of Events**

All events must be assessed to determine the following:

- If the event meets the criteria of an SAE as defined in Section 12.1.2.
- The relationship of the event to study treatment as defined in Section 12.2.2.
- The severity of the event as defined in Section 12.2.3.

### **12.2.2. Relationship of Events to Study Treatment**

The following definitions should be considered when evaluating the relationship of AEs and SAEs to the study treatment:

CONFIDENTIAL

The information contained herein may not be used, disclosed, or published without the written consent of Biogen MA Inc.

Relationship of Event to commercial drug	
Not related	An AE is considered “not related” to the use of the investigational drug if there is not a possibility that the event has been caused by the product under investigation. Factors pointing toward this assessment include, but are not limited to: the lack of reasonable temporal relationship between administration of the drug and the event, the presence of a biologically implausible relationship between the product and the AE (e.g., the event occurred before administration of drug), or the presence of a more likely alternative explanation for the AE.
Related	An AE is considered “related” to the use of the investigational drug if there is a possibility that the event may have been caused by the product under investigation. Factors that point toward this assessment include, but are not limited to: a positive re-challenge, a reasonable temporal sequence between administration of the drug and the event, a known response pattern of the suspected drug, improvement following discontinuation or dose reduction, a biologically plausible relationship between the drug and the AE, or a lack of an alternative explanation for the AE.

### 12.2.3. Severity of Events

The following definitions should be considered when evaluating the severity of AEs and SAEs:

Severity of Event	
Mild	Symptom(s) barely noticeable to subject or does not make subject uncomfortable; does not influence performance or functioning; prescription drug not ordinarily needed for relief of symptom(s) but may be given because of personality of subject.
Moderate	Symptom(s) of a sufficient severity to make subject uncomfortable; performance of daily activity is influenced; subject is able to continue in study; treatment for symptom(s) may be needed.
Severe	Symptom(s) cause severe discomfort; symptoms cause incapacitation or significant impact on subject’s daily life; severity may cause cessation of treatment with study treatment; treatment for symptom(s) may be given and/or subject hospitalized.

### 12.2.4. Expectedness of Events

Expectedness of all AEs will be determined by Biogen Safety and Benefit-Risk (SABR) according to the approved local label.

## 12.3. Monitoring and Recording Events

### 12.3.1. Adverse Events

Any AE experienced by the subject between the time of first dose of study treatment and End of Study or Early Termination is to be recorded on the subject’s CRF, regardless of the severity of the event or its relationship to study treatment.

CONFIDENTIAL

The information contained herein may not be used, disclosed, or published without the written consent of Biogen MA Inc.

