## 4.2. Schedule of Assessments

The schedule of assessments is presented in [Table 1](#). Assessment time points include an enrollment visit, a baseline visit, and follow-up visits at Months 1, 3, 4, 6, 9 and 12. An additional safety assessment will be performed remotely 4 months after the last study treatment dose. Subjects who discontinue treatment early will still be evaluated during the safety follow-up visit (i.e., 4 months after treatment and study discontinuation). Subjects having tentative disability progression identified near the end of the core study (e.g., Month 12) will attend additional follow-up visits 12 and 24 weeks later to confirm progression.

Magnetic resonance imaging (MRI) scans will be performed at the enrollment visit (no later than 7 days prior to the first dose of daclizumab), and at Months 1, 4, 6 and 12. MRI scans will be performed under the supervision of a trained radiologist. Ad-hoc MRI scans may be performed as needed, such as in the event of a MS relapse, in order to rule out a progressive multifocal leukoencephalopathy (PML) diagnosis.

Blood chemistry and hematology assessments will be performed at baseline and at Months 1, 3, 6, 9 and 12. Hematology assessments will include a complete blood count (CBC). Liver function tests (LFT) [alanine transaminase (ALT)/ aspartate transaminase (AST)] will be done at enrollment and monthly visits. Bilirubin testing must be done together with the first AST/ALT test at the enrollment visit. Bilirubin testing must also be done if ALT/SGPT (serum glutamic pyruvate transaminase), or AST/SGOT (serum glutamic oxaloacetic transaminase)  $>3*$ upper limit of normal (ULN), since treatment must be permanently discontinued with the concomitant elevation of total bilirubin  $>2*ULN$ .

At the end of the study, liver monitoring will be done per routine clinical practice.

A safety follow-up visit at 4 months after the last dose of daclizumab provided by the study will be conducted remotely to evaluate potential delayed safety outcomes. The assessments during the additional safety follow-up period will include all safety endpoints described in [Table 1](#). Liver function tests (LFT) will be performed only if the subject is continuing daclizumab or if the subject is within 4 months since study treatment discontinuation, and monitoring is deemed appropriate by the Investigator.

CONFIDENTIAL

The information contained herein may not be used, disclosed, or published without the written consent of  

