## Efficacy and Safety of Daclizumab in Subjects with RRMS Switching from Natalizumab

1. Written informed consent must be obtained prior to start of the study.
2. Screening MRI should occur no later than 7 days prior to the first dose of daclizumab. For subsequent visits, MRI scan can be performed up to 4 days prior to the visit. Ad-hoc MRIs may be conducted as needed, such as in the event of a relapse to rule out PML diagnosis.
3. This is required only for females of child-bearing potential. A urine pregnancy test will be performed monthly.
4. Liver function tests (LFTs) are required to be performed monthly (either on-site or via home visits at Month 7, 8, 10 and 11, if applicable), and samples will be analyzed centrally for the purposes of this study. Results from either local or central LFT tests can be used for medical management of the patient and to determine whether dosing should continue or be suspended at the monthly dosing timepoint. In cases where local LFTs were performed, samples must also be collected for central analysis.
5. Liver function tests (LFTs) during the safety follow-up will be performed only if the subject is continuing daclizumab or if the subject is within 4 months since study treatment discontinuation, and monitoring is deemed appropriate by the Investigator; Abnormal AST/ALT values as described in the product label will lead to treatment suspension or discontinuation.
6. [REDACTED]
7. Samples will be analyzed centrally.
8. Daclizumab dosing will start at baseline and occur monthly until Month 11. Doses at baseline and Months 1, 2, 3, 4, 5, 6 and 9 will be administered in the clinic, and doses at Months 7, 8, 10 and 11 can be administered at home or in the clinic. Daclizumab dosing will not begin until a minimum of 28 days have passed since last natalizumab dose. Before a monthly dose of daclizumab is given, LFT results from a prior test performed within the previous 28 (+3) days must be reviewed by the Study Neurologist or their backup.
9. Subjects will be provided a dosing diary at the Month 6 and Month 9 visits to record observations for home dosing only; home dosing is possible for Month 7, 8, 10, and 11. A window of  $\pm 4$  days applies to daclizumab dose even if it is done at home; subjects should be appropriately instructed on daclizumab self-administration using the autoinjector.

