### **7.2. Overall Study Duration and Follow-Up**

The study will consist of a 28-day (+3 days) screening period for each subject, a 12-month treatment period, and a 4-month remote safety follow-up visit after the subject's last treatment injection. The end of the study for each subject will be the last study visit or the visit at which the subject discontinues from the study (before the 12-month visit). Each follow-up visit will include a 4-day window before and after the visit for completion of all assessments. The follow-up period will include efficacy and safety following treatment initiation of daclizumab. The end of the study overall will be defined as the end of the 12-month study follow-up period for the last patient. The 4-month safety follow-up visit will be conducted remotely after the 12-month study follow-up visits have been completed.

Subjects having tentative disability progression identified near the end of the core study (e.g., Month 12) will attend additional follow-up visits 12 and 24 weeks later to confirm progression.

Subjects may discontinue treatment at any time during the study, and they will be followed for an additional 4 months to collect data on safety, LFT, MS treatment, relapses, and the use of concomitant medications.

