### 12.3.2. Serious Adverse Events

Any SAE experienced by a subject after the subject signs the ICF and before End of Study or Early Termination, is to be recorded on an SAE Form, regardless of the event relationship to daclizumab. For reporting timelines and procedures, see Section 12.3.3.

Subjects will be followed for all SAEs until the end of the 4 month safety follow-up. Thereafter, the event should be reported to Biogen SABR or designee only if the Investigator considers the SAE to be related to study treatment.

Any SAE ongoing when the subject completes the study or discontinues from the study will be followed by the Investigator until the event has resolved, stabilized, or returned to baseline status.

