5.4.1 Clinical Adverse Events

Treatment-emergent adverse event (TEAE) is defined as an adverse event having onset date on or after the first dosing date and prior to the 180 days after the last dosing date, or if it was present prior to start of study treatment and subsequently worsened. If it cannot be determined whether an event is treatment emergent due to a missing or partial date, then the event will be tabulated as treatment emergent. Adverse events will be coded using the Medical Dictionary for Regulatory Activities (MedDRA). Only treatment-emergent adverse events (TEAE) will be presented in the summary tables.

In general, AE tables include the following (but not limited to):

- incidence of treatment-emergent adverse events will be summarized overall and by severity (mild, moderate and severe);
- TEAE's will also be presented by system organ class (SOC) and preferred terms (PT) and sorted by decreasing frequency of PT within SOC, if there is sufficient data. If a patient experiences an event more than once with varying severity during the study, he/she will be counted only once with the maximum severity within each SOC and PT;
- the incidence of serious adverse events (SAE) will be summarized by system organ class (SOC) and preferred terms (PT) and sorted by frequency if there is sufficient data; otherwise listings for individual patients who experienced SAEs will be generated;
- any incidence of adverse events that lead to the dose interruption, discontinuation of study drug or premature withdrawal from the study will be presented; a listing of these adverse events may also be presented;
- any deaths that occurred during the study will be listed and relevant information including timing of the death relative to study treatment, reason of death, concomitant medications, the investigator assessment of the cause of death will be provided;
- incidences of adverse events of special interest (AESI) will also be presented, if there is sufficient data; otherwise listings of AESI will be generated. These adverse event of special interest categories are defined mainly based on Standardized MedDRA Queries (SMQs), SOC's, and/or PT's. The AEs of special interest categories may include but are not limited to the following:
 - Infections, including serious infections and potential opportunistic infections
 - Cutaneous events, including serious events
 - Hepatic disorders
 - Gastrointestinal events
 - Autoimmune disorders
 - Injection site reactions

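### The stated cut-off for recording AEs and SAEs conflicts with the 4-month safety follow-up, and for subjects who leave the study early it falls before that visit

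*Protocol*

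**What the plan says.** **Text that closes recording.**
- Protocol Section 12.3.1 limits case report form entries to "Any AE experienced by the subject between the time of first dose of study treatment and End of Study or Early Termination".
- The first paragraph of Section 12.3.2 applies the same end point to the SAE Form. The reporting text under Section 12.3.3 applies it to 24-hour SAE reporting, where it is called the Early Termination Visit.
- Section 7.2 gives two definitions. For a subject: "The end of the study for each subject will be the last study visit or the visit at which the subject discontinues from the study". For the trial: "The end of the study overall will be defined as the end of the 12-month study follow-up period for the last patient". It places the safety visit after the 12-month visits.

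**Text that keeps collection open.**
- Section 4.2 says the 4-month visit is "conducted remotely to evaluate potential delayed safety outcomes", covers all the safety endpoints of Table 1, and is still done for subjects who discontinue early. Section 11.2.2.3 repeats the purpose.
- Section 7.2 says subjects who stop treatment are followed for 4 more months, with safety data among the items collected.
- In Table 1 the AE/SAE row is a single entry covering the whole study. The Month 15 safety visit is Visit 9 and early discontinuation is a separate Visit 10.
- The second paragraph of Section 12.3.2 says: "Subjects will be followed for all SAEs until the end of the 4 month safety follow-up". There is no matching sentence for non-serious AEs.

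**SAP.** Section 5.4.1 counts an event as treatment-emergent if its onset is on or after the first dose and "prior to the 180 days after the last dosing date". Section 4.1 takes the last visit date as end of study. Section 5.4 uses data from the entire study period. Section 2 says the abbreviated report will draw on the safety follow-up.

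**The concern.** The remote visit exists to find delayed events. If a site follows Section 12.3.1 to the letter, a subject who has left at an early termination visit has a closed AE record by the time that visit takes place. A completer's record is closed too if the site takes Month 12 as the end of study. Another site, working from Table 1 or Section 4.2, would keep recording. The same delayed event could then appear in the safety tables from one site and be absent from another.

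The events at risk are mainly non-serious ones, because only SAEs have a sentence carrying them through the follow-up. The SAP's categories of special interest include hepatic, cutaneous and autoimmune events. The SAP says the sponsor terminated the study after about 30 subjects were enrolled. In a data set of that size, a few events recorded at some sites and not at others would change the tables.

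**Working it through.** **Inputs.**
- Last scheduled dose at Month 11 (Table 1, footnote 8): "Daclizumab dosing will start at baseline and occur monthly until Month 11".
- Safety visit 4 months after the last dose, in the Month 15 column, ±14 days (Table 1 and footnote 13).
- Month 12 visit ±4 days (Table 1) and dose window ±4 days (footnote 9).
- Treatment-emergent window of 180 days after the last dose (SAP Section 5.4.1).
- Assumption: 1 month = 365.25/12 = 30.44 days, with 28-day months as a variant.
- Assumption: an early leaver's termination visit falls 0 to 30 days after the last dose. The documents give no figure for this.

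**Step 1. Reproduce the plan's timing.** Month 11 + 4 months = Month 15, as in Table 1. Screening of 28 to 31 days is 0.92 to 1.02 months. Adding 15 gives 15.9 to 16.0 months, which agrees with the stated participation of up to 16 months.

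**Step 2. Days of AE recording after the last dose.**

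| Case | Days recorded | Share of 180 days | Unrecorded days of the 122-day follow-up |
|---|---|---|---|
| Completer, recording ends at Month 12 | 30.4 | 30.4/180 = 17% | 121.75 − 30.4 = 91 |
| Completer, recording ends at Month 15 | 4 × 30.44 = 121.75 | 121.75/180 = 68% | 0 |
| Early study leaver, Section 12.3.1 followed | 0 to 30 (assumed) | 0% to 17% | 91 to 122 |

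The two ±4-day windows move the first row between 30.4 − 8 = 22 and 30.4 + 8 = 38 days. With 28-day months the completer figures are 28 days (16%) and 112 days (62%).

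**Step 3. What remains of the SAP window after the last scheduled contact.** 180 − 121.75 = 58 days. With the ±14-day visit window this is 44 to 72 days. With 28-day months it is 180 − 112 = 68 days (54 to 82). This gap exists on either reading of Section 12.3.1.

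**Step 4. Can the text be reconciled as it stands?** For a completer, yes, if the last study visit in Section 7.2 means Visit 9. For an early leaver, no. Section 7.2 ends that subject's study at "the visit at which the subject discontinues from the study", and Table 1 makes early discontinuation a separate visit. Section 4.2 nevertheless places the safety visit 4 months after treatment and study discontinuation. Recording throughout the study, as Table 1 has it, does not settle the matter, because it depends on when the study ends for that subject.

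**The case against.** The best defence is that the plan as a whole clearly intends safety collection through the follow-up. Visit 9 can be read as the last study visit. Section 4.2 includes every Table 1 safety endpoint in the follow-up, Section 7.2 promises 4 more months of safety data, and the SAP's end of study is the last visit date. SAEs are largely protected by the second paragraph of Section 12.3.2, which restricts reporting to related events only after the follow-up ends. On this view Section 12.3.1 needs a clarification and nothing has been lost.

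Much of that stands. It shows that the defect is a contradiction between instructions rather than a settled absence of collection, and that SAEs are less exposed. It does not help the early study leaver, for whom Section 12.3.1 names an end point before the safety visit.

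Stronger inferences that a reader might draw are not supported:
- **That AE incidence is biased low.** The calculation counts days, not events. It cannot show how many events would be missed, and sites may have recorded through the follow-up.
- **That everyone who stops treatment early is worst affected.** Stopping treatment differs from leaving the study. Under Section 9.2, subjects off dose stay under data collection, so those who remain in the study have more recording after the last dose than a completer does on the narrow reading. On that reading even study leavers lose at most about 30 days more than completers.
- **That nearly every subject left early because the sponsor terminated the study.** The SAP gives about 30 enrolled and limited follow-up, but no count of completers.
- **That the SAP claims complete ascertainment to day 180.** Section 5.4.1 classifies recorded events. It does not say that collection runs that long.

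**Conclusion.** The conflict is real and worth correcting. Sections 12.3.1 and 12.3.2 and the reporting text under 12.3.3 state a cut-off that contradicts Sections 4.2, 7.2 and 11.2.2.3, Table 1 and Section 12.3.2's own second paragraph. For early study leavers the cut-off precedes the visit meant to detect delayed events. For completers the text is ambiguous. The consequence is a risk of incomplete or uneven recording, mainly of non-serious AEs, and not a demonstrated bias.

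The possible loss for a completer is the difference between about 30 and about 122 days of recording. An early leaver has about 0 to 30 days, and that range rests on an assumed timing of the termination visit. Separately, and on any reading, roughly the last 58 days of the SAP window have no scheduled AE collection for most subjects.

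**What to change.** **Protocol.** In Sections 12.3.1, 12.3.2 and 12.3.3, state that all AEs and SAEs are recorded to the end of the 4-month safety follow-up, and that this includes subjects who terminate the study early. The visit is already scheduled, so the cost is a few sentences and a few more AE entries.

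**SAP.** Keep the 180-day window. Shortening it to match the visit (121.75 + 14 = about 136 days) would drop events that the plan can legitimately collect between days 136 and 180:
- events in subjects with tentative progression, whose 24-week visit falls about 30 + 168 = 198 days after a Month 11 dose;
- events in subjects who stop dosing but stay in the study;
- related SAEs, which remain reportable after the follow-up.

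Instead, add a note to the safety tables that scheduled AE collection ends about 4 months after the last dose, so that roughly the last 58 days of the window (44 to 72 with the visit window) have no scheduled collection for most subjects. This costs one footnote.
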